#### 5.1.1 Inclusion criteria

1. Diagnosis of ADA-SCID confirmed by DNA sequencing OR by confirmed absence of <3% of ADA enzymatic activity in peripheral blood or (for neonates) in umbilical cord blood erythrocytes and/or leucocytes or in cultured foetal cells derived from either chorionic villus biopsy or amniocentesis, prior to institution of PEG-ADA replacement therapy
2. Patients who lack a fully HLA-matched family donor
3. Patients (male or female) < 5years of age OR  
  
Patients (male or female) ≥ 5years to 15rs of age who have preserved thymic function as evidenced by presence of >10 % naïve T cells (CD4+45RA+27+ cells)
4. Parental/guardian signed informed consent

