#### 5.1.2 Exclusion criteria

1. Cytogenetic abnormalities on peripheral blood
2. Evidence of active malignant disease
3. Known sensitivity to busulfan
4. If applicable, confirmed pregnancy (to be tested in patients above 12 years old)

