#### **Inclusion criteria**

1. Diagnosis of ADA-SCID confirmed by DNA sequencing OR by confirmed absence of <3% of ADA enzymatic activity in peripheral blood or (for neonates) in umbilical cord blood erythrocytes and/or leucocytes or in cultured foetal cells derived from either chorionic villus biopsy or amniocentesis, prior to institution of PEG-ADA replacement therapy
2. Patients (male or female) between 0-18 years at time of treatment
3. Patient treated with allogeneic haematopoietic stem cell transplantation since 2000

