### **8.3 Treatment failure/lack of response**

- Failure of immune reconstitution is determined by poor recovery of T lymphocyte numbers and function by day 180

OR

- by absence of gene corrected cell engraftment (<0.1 %) tested by quantitative PCR in peripheral blood and/or BM samples 6 months after the procedure.
- If there is no immune recovery/evidence of gene modified cell engraftment seen 180 days after gene therapy, PEG-ADA will be commenced OR the patient will undergo stem cell transplant from a matched unrelated donor depending on the clinical state of the child.
- If there is no matched unrelated donor available, the patient will be commenced on PEG-ADA OR if the referring health agency is unable to provide funding, the patient will undergo stem cell transplant from an unrelated or haploidentical parental donor.
- In the absence of a matched family or unrelated donor a second administration of the gene therapy treatment could be considered following specific approval from GTAC/MHRA on a case by case basis.

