### HSCT Control Patients

The primary efficacy population from the HSCT historical control cohort will consist of ADA-SCID patients without a medically eligible HLA-matched sibling/family donor and treated with HSCT at Great Ormond Street Hospital (GOSH) from the year 2000 onwards.

Secondary efficacy populations will comprise:

- ADA-SCID patients with matched related donors treated with HSCT at GOSH from the year 2000 onwards;
- the complete HSCT historical control cohort consisting of ADA-SCID patients with any type of donor treated with HSCT at GOSH from the year 2000 onwards.

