### **8.2.3 Disease Treatment History**

Number (%) of IMP treated subjects who previously received PEG-ADA treatment, receiving immunoglobulin replacement therapy, receiving infection prophylaxis, any previous BM or PBSC transplant (with the outcome) will be summarized.

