### **8.2.15 Transplant Details for the HSCT Controls**

For the HSCT control groups, the age in months at transplant will be recorded on the eCRF.

Age (months) at transplant, number of CD34+ cells/kg transplanted and busulfan dose, if appropriate, will be summarized for each HSCT control group using descriptive statistics.

Number (%) of subjects with each type of transplant cells, transplant donor type, conditioning type, receiving enzyme replacement therapy (ERT) prior to the transplant, receiving ERT after the transplant, receiving IgRT prior to the transplant, receiving IgRT after the transplant and receiving gene therapy after the transplant will be summarized for each HSCT control group.

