### **8.3.1.2 Event-free Survival at 12 Months**

Event-free survival will be evaluated using the time in months from transplant to either the first event or their last evaluation calculated as:

$$12 * (\text{date of event/last evaluation} - \text{date of transplant}) / 365.25,$$

or, for HSCT control subjects for whom the dates were not recorded, as:

$$\text{age in months at death/end of follow-up} - \text{age in months at transplant}.$$

For the purpose of this analysis, the events of interest are:

- death;
- reinstitution of PEG-ADA ERT;
- requirement for a second transplant.

Event-free survival will be summarized in the same way as overall survival described in Section 8.3.1.1.

In addition, if there are any events (other than death), the time to each event will be summarized in a similar manner to the overall event-free survival.

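### The HSCT control group has no index-transplant or prior-gene-therapy rule, and EFS does not say how gene therapy after HSCT is scored

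*Protocol*

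**What the plan says.** **Who is a control.** Protocol 5.3 asks for the diagnosis, age 0-18 and "Patient treated with allogeneic haematopoietic stem cell transplantation since 2000". In SAP 7.1 the primary control group is the subset treated at the site without a matched sibling or family donor. Appendix 8 collects transplants from 2000 to 2016, while SAP 7.1 leaves the end date open.

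**Who is a trial subject.** Protocol 5.1.1 requires "Patients who lack a fully HLA-matched family donor", the same donor situation as the primary controls. The four exclusions in 5.1.2 do not include earlier HSCT or earlier gene therapy.

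**What crossing the plan expects.** For IMP subjects, SAP 8.2.3 says that "any previous BM or PBSC transplant (with the outcome) will be summarized". For controls, SAP 8.2.15 says that the numbers "receiving IgRT after the transplant and receiving gene therapy after the transplant will be summarized for each HSCT control group". After failed gene therapy, Protocol 8.3 says "PEG-ADA will be commenced OR the patient will undergo stem cell transplant from a matched unrelated donor".

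**What counts as an event.** SAP 8.3.1.2 lists death, a return to PEG-ADA and "requirement for a second transplant". Appendix 8, section 5, is similar. Neither mentions gene therapy, as an event or as a reason for censoring.

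**The concern.** The comparison of 12-month OS and EFS between IMP subjects and HSCT controls is part of the primary objective. It needs a clear starting treatment for each child, groups that do not share members, and one reading of what a failure is. The plan foresees children who receive both treatments but gives no analysis rule for them. Three readings are open:

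- A child whose gene therapy failed and who then had an unrelated-donor HSCT at the site meets every control criterion. A child whose first HSCT was before 2000 or elsewhere can likewise enter at a repeat transplant.
- A child with HSCT first and the IMP later can be in both primary groups. The log-rank test and the confidence interval for the difference treat the groups as independent.
- A failed HSCT rescued directly by gene therapy can be scored event-free.

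With 10 IMP subjects and probably a small control group, a single child scored one way or the other is visible in the result.

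**Working it through.** The plan states no sample-size, power or event figure on this point, so there is nothing to reproduce. The check is first on the text, then on the influence of one child.

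**Text**

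1. *Overlap is possible in the primary comparison.* SAP 8.3 compares on-study IMP subjects with controls lacking a matched related donor. The donor criteria coincide, all treatment is at one site, and no rule makes the groups exclusive.
2. *Gene therapy before the control HSCT may go unseen.* SAP 8.2.15 tabulates gene therapy after the transplant only. The data list in Appendix 8, section 3, does not name earlier gene therapy; it could appear only under general medical history.
3. *The third EFS event is ambiguous.* SAP 8.2.14 uses the word transplant for the IMP infusion, so a second transplant could include gene therapy. SAP 8.2.15 lists gene therapy after the transplant as a separate item, which points the other way.
4. *PEG-ADA closes part of the gap.* A control who restarts PEG-ADA before gene therapy already has an event. The gap remains where PEG-ADA was not restarted.
5. *No planned analysis picks this up.* The sensitivity analyses in SAP 8.3.4 run only if major protocol violations have occurred. Overlap violates nothing.

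**Influence of one child**

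Inputs: 10 on-study subjects (SAP 7.1). The control number N is not given; N = 5, 10, 15 and 20 are assumed. If one control rescued by gene therapy within 12 months is scored as an event instead of event-free, control EFS falls by 1/N:

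- N = 5: 1/5 = 20 points
- N = 10: 1/10 = 10 points
- N = 15: 1/15 = 6.7 points
- N = 20: 1/20 = 5 points

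Illustration with N = 10, IMP EFS assumed 10/10, and control EFS starting at 7/10 (near the 67% matched-unrelated-donor survival in Protocol 5.1.3). Intervals are exact 95%; Fisher's exact test stands in for the log-rank test.

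- None reclassified: 7/10 (34.8% to 93.3%), difference 30 points, p = 0.21
- One reclassified: 6/10 (26.2% to 87.8%), difference 40 points, p = 0.087
- Two reclassified: 5/10 (18.7% to 81.3%), difference 50 points, p = 0.033

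Removing one event-free dual-group child from the IMP arm changes 10/10 (lower limit 69.2%) to 9/9 (lower limit 66.4%). The point estimate does not move. If gene therapy comes after month 12, the 12-month EFS count changes by 0.

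**The case against.** The strongest reply is that much of this may already be handled. The SAP calls the IMP infusion a transplant, so gene therapy after HSCT may count as a second one. A restart of PEG-ADA is already an event. Previous transplant and later gene therapy are both tabulated, so some overlap would be visible. A gene-therapy failure does not leave the IMP arm: it stays there and counts as an event if PEG-ADA is restarted or a transplant is needed. Under the 2000-2016 window of Appendix 8, a rescue transplant after 2016 could not enter the control group. Keeping survival after rescue with the initial treatment is ordinary OS practice. Protocol 8.9.2 describes the comparisons with historical controls as descriptive.

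Most of this stands, and it limits the point. It does not settle how a directly rescued control is scored, which transplant starts the clock, or what happens to a child eligible for both groups. Tabulating crossings does not supply an analysis rule.

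A reader might also infer that crossing is common from the protocol's own figures: 119 - 106 = 13 repeat transplants (13/119 = 11%, Protocol 3.2.1), and 36 - 25 = 11 earlier gene-therapy patients not off enzyme (11/36 = 31%, Table 1), 4 of 8 of them at this site. The documents do not support that. The first figure is HSCT followed by HSCT in a multicentre series with all donor types. The second counts patients not off enzyme after gammaretroviral therapy, and no rescue HSCT at this site is reported among them. Neither measures crossing between these two groups.

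**Conclusion.** The gap is real and should be fixed. The control index treatment is undefined, earlier gene therapy is not excluded, and the EFS list does not say how gene therapy after HSCT is scored.

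Two stronger statements might be inferred and do not hold. One is that a control rescued by gene therapy is never an EFS event; a PEG-ADA restart, or a broad reading of transplant, may capture it. The other is that every crossing child distorts the primary comparison. Compassionate-use children enter only the secondary comparisons, and gene therapy after month 12 leaves 12-month EFS unchanged.

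The EFS omission, where it applies, raises control EFS and so works against the IMP. The direction for failed gene-therapy patients entering as controls is unknown: Protocol 5.1.3 says a later transplant is not compromised, while 9.2.5 says it may be. The net effect cannot be signed.

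The 5 to 20 points per child rest on assumed control numbers. The p-values also rest on assumed outcomes and only show sensitivity. No dual-group child is shown to exist.

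**What to change.** 1. **EFS.** In SAP 8.3.1.2 and Protocol Appendix 8, section 5, change the third event to *second transplant or gene therapy after the index treatment*, applied to both arms. For controls without dates, record the age at that event; the fallback formula in 8.3.1.2 uses only age at death or end of follow-up.
2. **Control index.** In Protocol 5.3 and SAP 7.1, define the control index as the child's first allogeneic HSCT, at the site since 2000, with no earlier gene therapy. Use it as the time origin.
3. **Overlap.** Keep the on-study primary population of 10 unchanged and keep OS with the initial treatment. Report how many children are eligible for both groups. Repeat OS and EFS excluding them, and again excluding IMP subjects with a previous HSCT.

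Reassigning on-study subjects to an HSCT arm is not advised: it would alter a prespecified population of 10 after recruitment, so exclusions belong in the sensitivity analysis only.

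The cost is mainly wording. A few repeat transplants may drop out of the control group, and earlier gene therapy in controls needs a check of site records.

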### **5.4 Concomitant medication**

Entry into this study will not affect concomitant treatments for ADA-deficiency, such as prophylactic antibiotics or intravenous gamma globulin therapy. However, the patient will be

withdrawn from cotrimoxazole prophylaxis at least day -1 prior to IMP infusion. Cotrimoxazole will be restarted when ANC > 1 x 10^9/l on 3 consecutive days after reinfusion of transduced cells. Aerosolised or intravenous pentamidine will be used as prophylaxis for *Pneumocystis jirovecii* in the intervening time period.

PEG-ADA will be continued until one month (+/- 6 days) post-infusion of gene-modified cells. PEG-ADA will be restarted if i) the child is withdrawn from the study ii) if after 180 days there is no evidence of gene modified cell engraftment and/or failure of T cell recovery.

PEG-ADA may be restarted at PIs discretion prior to this time point on clinical grounds e.g infective problems or delayed T cell reconstitution.

## 6 Enrolment of subjects

Patients will be enrolled following diagnosis and referral to GOSH. ADA is an inherited disease and infants normally present in the first year of life. Patients less than 5 years of age will be enrolled and also those >5 years who show evidence of thymic function will also be eligible for enrolment. Informed consent will be obtained from parents/guardians and assent where appropriate.

The Chief/Principal investigator will discuss the study at length with the parent/guardian of a potential new subject. A printed information leaflet will be supplied and the parent/guardian given ample time to consider his/her decision. The parent/guardian will be encouraged to ask further questions about the study to the Investigator or the clinical nurse specialist. Interpreters will be used if English is not the native tongue. Patient Information Leaflet (PILs) will be translated into native language.

Should a parent/guardian decide that the patient will participate they will be invited to sign the study consent form.

Consent will take place prior to any study specific procedures.

Once a patient has been enrolled onto the study, the ADA-SCID pre-gene therapy patient protocol (see Appendix 4 for details) will be completed, reviewed, signed off by the investigator and distributed to all concerned parties.

## 7 Treatment protocol

### 7.1 Informed consent procedure

ADA deficiency is an inherited disease and therefore most patients with this inherited disease are diagnosed while they are still infants and are therefore incapable of giving informed consent. Therefore, it is expected that the majority of the informed consent will be obtained from parents/guardians by the Chief investigator or co-investigator.

The Chief investigator/co-investigator will discuss the study at length with the parent/guardian of a potential new subject, including an explanation of the aims, methods, anticipated benefits and potential risks of the study. The Chief investigator/co-investigator will explain that the patients are under no obligation to enter the trial and that they can withdraw at any time during the trial, without having to give a reason.

A patient information leaflet will be supplied and the parent/guardian will be given ample time to consider his/her decision. The parent/guardian will be encouraged to ask further questions about the study to the Investigator or the clinical nurse specialist.

Should a parent/guardian decide that the patient will participate they will be invited to sign the study consent form. A copy of the patient information leaflet and signed consent form will be provided to the patient to take home. A further copy will be retained in the patient's medical notes and the original will be filed in the Trial Master File.

Informed consent will be obtained before any trial-related procedures are performed.

### 7.2 Randomisation procedures

This section is not applicable as the trial is non-randomised.

### 7.3 Emergency unblinding

This section is not applicable as this is an open-label trial.

### 7.4 Screening assessments

The first part of the study will involve performing laboratory tests to determine whether the subject meets the inclusion criteria and does not have a contraindication which would exclude them from the trial.

## 7.5 Treatment procedures

### 7.5.1 Harvest of a back-up autologous graft

If a back-up has not previously been stored, haematopoietic stem cells will be collected from the patient as a back-up at the time of leukapheresis (on day -3) or bone marrow harvest (on day -2) (see section 7.5.2). A back-up of  $3 \times 10^6$  CD34+/kg will be stored.

The total cell count required for both back-up ( $3 \times 10^6$  CD34+ cells/kg) and for transduction ( $1 \times 10^6$  CD34+ cells/kg) is  $4 \times 10^6$  CD34+ cells/kg.

If insufficient cells are collected then the total collection will be stored as back-up, the patient will be withdrawn from the trial and a further collection will be attempted 2-3 months later in order to meet the criteria specified above.

The back-up cells serve as a salvage procedure, should there be a lack of haematopoietic recovery observed following the injection of genetically-manipulated cells (back-up graft).

The bone marrow or leukapheresis cells will be frozen and stored un-manipulated in liquid nitrogen vapours (-162°C and -180°C) to constitute the back-up graft. The back-up will be used in case the final cell dose is very low as specified or if no haematopoietic recovery is observed after 6 weeks, following the gene therapy treatment.

### 7.5.2 CD34+ cells for gene therapy

CD34+ cells for the gene therapy will be obtained preferably by leukapheresis (possibly augmented with Plerixafor) of G-CSF mobilised peripheral blood stem cells (PBSCs). If PBSC leukapheresis is not clinically appropriate or is contraindicated or where mobilisation fails, a bone marrow harvest will be performed. PBSCs are the preferred choice since we will obtain far higher numbers of CD34+ cells which in turn will allow gene modification of larger stem cell numbers prior to reinfusion into the patient. Autologous cells will be stored if cell count is  $>4 \times 10^6$  CD34+ cells/kg (back-up:  $3 \times 10^6$  CD34+ cells/kg and cells for transduction:  $1 \times 10^6$  CD34+ cells/kg).

For PBSC collection, recombinant human granulocyte colony stimulating factor (rhu G-CSF) will be administered by subcutaneous injection (usually in the abdominal region) for 5 to 6 successive days (dose 5-16 µg/kg per day) (possibly augmented with Plerixafor) prior to harvest. CD34+ cell counts will be monitored from day 5, and leukapheresis performed on days 5 and/or 6 providing that the CD34+ cell count is greater than  $1 \times 10^4$ /ml. If a bone marrow harvest is to be used as the source of CD34+ cells, bone marrow will be harvested from the patient under general anaesthesia from the posterior iliac crests on both sites by multiple punctures. The amount of marrow collected will be equivalent to 20 ml/kg of body weight. This

will give a total nucleated cell count of greater than  $10^8$  cells/kg. This in turn should yield a CD34+ cell dose of greater than  $10^6$  cells/kg after CD34+ cell selection.

Patients from whom  $<1 \times 10^6$  CD34+ cells/kg are available, will be withdrawn from the study prior to conditioning. A repeat harvest will be considered after a period of 2-3 months and the patient will be re-enrolled onto the study.

Patients withdrawn from the study prior to administration of transduced CD34+ cells will resume normal clinical care. Efficacy and safety assessments will not be carried out from the point of withdrawal and data will not be recorded in the Case Report Forms (CRFs).

### **7.5.3 CD34+ cell purification**

CD34+ cells will be separated by standard CliniMACs cell purification protocols which are in routine use as part of the bone marrow transplantation programme. Operating procedures are available on request. Purified cells will be immediately transferred to the gene therapy laboratory for transduction.

### **7.5.4 CD34+ cell culture and transduction**

CD34+ cells will be purified, cultured and transduced in a dedicated clinical gene therapy laboratory at Great Ormond Street Hospital. CD34+ cells will be purified using standard protocols for stem cell transplantation (CliniMACs), and seeded into fresh closed cell culture bags or flasks in serum free medium (X-VIVO-20, Lonza) supplemented with 1% human serum albumin (HSA, Baxter), and cytokines IL-3 (20ng/ml), SCF (300ng/ml), Flt-3 ligand (300ng/ml), TPO (100ng/ml), at a density of  $0.5 - 1 \times 10^6$ /ml. All cytokines (Peprotech) and culture reagents are approved for ex vivo clinical use. A small culture sample will be removed for sterility testing. After ~18 hours total pre-stimulation, cells will be cultured with EF1αS-ADA lentiviral vector supernatant for 24 hours in the same complete media at a cell concentration of  $0.5 - 1 \times 10^6$ /ml. Following transduction, a portion of cells will be removed for quality control (analysis of transduction efficiency, viability, sterility, RCL). The remaining cells will be resuspended in Human Serum Albumin (HSA) 2% in order to be administered to patient.

### **7.5.5 Testing prior to patient re-infusion**

Samples are collected during and at the end of the procedure for cell viability (trypan blue stain, 7AAD staining) and sterility (for bacteria, fungi and mycoplasma). Transduction efficiency (transgene PCR), and RCL testing will be performed after infusion of cells and recorded retrospectively.

### **7.5.6 Patient conditioning regimen**

During transduction of CD34+ cells, patient will commence conditioning. Patients will receive non-myeloablative conditioning with intravenous busulfan. Busulfan dose will be weight-dependent, in accordance with the recommendation below (table taken from (Bartelink et al., 2012)).

Body-weight	mg/kg/day
3 to 15kg	5.1
15 to 25kg	4.9
25 to 50kg	4.1
50 to 75kg	3.3
75 to 100kg	2.7

A wash-out period of at least 24 hours will be maintained prior to reinfusion of the transduced cells. Pharmacokinetic monitoring of busulfan levels will be performed after administration of the first dose.

#### 7.5.7 Infusion of transduced cells

Cells will be washed and infused in a volume up to 20mls/kg intravenously over 30-45 minutes. A baseline set of observations will be carried out before the infusion begins (temperature, pulse, respirations, oxygen saturations). These will then be repeated 15 minutes into the infusion and then again at the end of infusion. Regular monitoring (frequency and duration dependent on reaction/occurrence) will be commenced if anything abnormal (e.g. allergic reaction) occurs during the infusion or if antihistamines are administered.

